13.2 Participant Information, Informed Consent, and Participant Authorization

Written consent documents will embody the elements of informed consent as described in the Declaration of Helsinki and the ICH Guidelines for GCP and will be in accordance with all applicable laws and regulations. The ICF, participant authorization form (if applicable), and

Page 57 of 64 30 Aug 2022

participant information sheet (if applicable) describe the planned and permitted uses, transfers, and disclosures of the participant's personal and personal health information for purposes of conducting the study. The ICF and the participant information sheet (if applicable) further explain the nature of the study, its objectives, and potential risks and benefits, as well as the date informed consent is given. The ICF will detail the requirements of the participant and the fact that he or she is free to withdraw at any time without giving a reason and without prejudice to his or her further medical care.

The investigator is responsible for the preparation, content, and IRB approval of the ICF and if applicable, the participant authorization form. The ICF, participant authorization form (if applicable), and participant information sheet (if applicable) must be approved by both the IRB and the sponsor prior to use.

The ICF, participant authorization form (if applicable), and participant information sheet (if applicable) must be written in a language fully comprehensible to the prospective participant. It is the responsibility of the investigator to explain the detailed elements of the ICF, participant authorization form (if applicable), and participant information sheet (if applicable) to the participant. Information should be given in both oral and written form whenever possible and in the manner deemed appropriate by the IRB. In the event the participant is not capable of rendering adequate written informed consent, then the participant's legally acceptable representative may provide such consent for the participant in accordance with applicable laws and regulations.

The participant, or the participant's legally acceptable representative, must be given ample opportunity to: (1) inquire about details of the study and (2) decide whether or not to participate in the study. If the participant, or the participant's legally acceptable representative, determines he or she will participate in the study, then the ICF and participant authorization form (if applicable) must be signed and dated by the participant, or the participant's legally acceptable representative, at the time of consent and prior to the participant entering into the study. The participant or the participant's legally acceptable representative should be instructed to sign using their legal names, not nicknames, using blue or black ballpoint ink. The investigator must also sign and date the ICF and participant authorization (if applicable) at the time of consent and prior to participant entering into the study; however, the sponsor may allow a designee of the investigator to sign to the extent permitted by applicable law.

Once signed, the original ICF, participant authorization form (if applicable), and participant information sheet (if applicable) will be stored in the investigator's site file. The investigator must document the date the participant signs the informed consent in the participant's medical record. Copies of the signed ICF, the signed participant authorization form (if applicable), and participant information sheet (if applicable) shall be given to the participant.

All revised ICFs must be reviewed and signed by relevant participants or the relevant participant's legally acceptable representative in the same manner as the original informed consent. The date the revised consent was obtained should be recorded in the participant's objectives, and potential risks and benefits, as well as the date informed consent is given. The ICF will detail the requirements of the participant and the fact that they are free to withdraw at any time without providing a reason and without prejudice to their other medical care.

Page 58 of 64 30 Aug 2022

The Investigator is responsible for the preparation, content, IRB approval of the ICF and, if applicable, the participant authorization form. The ICF, participant authorization form (if applicable), and participant information sheet (if applicable) must be approved by the IRB and the Sponsor prior to use

The ICF, participant authorization form (if applicable), and participant information sheet (if applicable) must be written in a language fully comprehensible to the prospective participant. It is the responsibility of the Investigator to explain the detailed elements of the ICF, participant authorization form (if applicable), and participant information sheet (if applicable) to the participant. Information should be given in both oral and written form whenever possible and in the manner deemed appropriate by the IRB. In the event the participant is not capable of rendering adequate written informed consent, the participant's legally acceptable representative may provide such consent for the participant in accordance with applicable laws and regulations.

The participant, or the participant's legally acceptable representative, must be given medical record, and the participant should receive a copy of the revised ICF.

13.3 Participant Confidentiality

The Sponsor and designees affirm and uphold the principle of the participant's right to protection against invasion of privacy. Throughout this study, a participant's source data will only be linked to the Sponsor's clinical study database or documentation via a unique identification number. As permitted by all applicable laws and regulations, limited participant attributes, such as sex, age, or date of birth, and participant initials may be used to verify the participant and the accuracy of the participant's unique identification number.

To comply with ICH Guidelines for GCP and to verify compliance with this protocol, the Sponsor requires the Investigator to permit its monitor or designee's monitor, representatives from any regulatory authority (e.g., FDA, Medicines and Healthcare products Regulatory Agency, Pharmaceuticals, and Medical Devices Agency), the Sponsor's designated auditors, and the appropriate IRBs to review the participant's original medical records (source data or documents), including, but not limited to, laboratory test result reports, ECG reports, admission and discharge summaries for hospital admissions occurring during a participant's study participation, and autopsy reports. Access to a participant's original medical records requires the specific authorization of the participant as part of the informed consent process (see Section 9.1.1).

Copies of any participant source documents that are provided to the Sponsor must have certain personally identifiable information removed (i.e., participant name, address, and other identifier fields not collected on the participant's eCRF).

13.4 Publication, Disclosure, and Clinical Trial Registration Policy

13.4.1 Publication and Disclosure

The Investigator is obliged to provide the Sponsor with complete test results and all data derived by the Investigator from the study. During and after the study, only the Sponsor may make study information available to other study Investigators or regulatory agencies, except as required by law or regulation. Except as otherwise allowable in the clinical study site agreement, any public

Page 59 of 64 30 Aug 2022

disclosure (including publicly accessible websites) related to the protocol or study results, other than study recruitment materials and/or advertisements, is the sole responsibility of the Sponsor.

The Sponsor may publish any data and information from the study, including data and information generated by the Investigator, without the consent of the Investigator. Manuscript authorship for any peer-reviewed publication will appropriately reflect contributions to the production and review of the document. All publications and presentations must be prepared in accordance with this section and the Clinical Study Site Agreement. In the event of any discrepancy between the protocol and the Clinical Study Site Agreement, the Clinical Study Site Agreement will prevail.

The Sponsor may publish any data and information from the study (including data and information generated by the Investigator) without the consent of the Investigator.

13.4.2 Clinical Trial Registration

In order to ensure that information on clinical trials reaches the public in a timely manner and to comply with applicable laws, regulations, and guidance, the Sponsor will register this clinical trial on ClinicalTrials.gov (and possibly on other publicly accessible websites) before the start of the study.

Sponsor contact information, along with the Investigator's city, state, country, and recruiting status, will be registered and available for public viewing. Once participants receive the Investigator's contact information, they may call the site and request enrollment into the trial. The investigative site(s) are encouraged to handle such trial inquiries according to their established participant screening process. If the caller asks additional questions beyond the topic of trial enrollment, they should be referred to the Sponsor.

13.4.3 Clinical Trial Results Disclosure

If required at the conclusion of the study, the Sponsor will post the results on ClinicalTrials.gov or other publicly accessible websites, as required by applicable national and local laws and/or regulations.

13.5 Insurance and Compensation for Injury

Each participant in the study must be insured in accordance with the regulations applicable to the site where the participant is participating. If a local underwriter is required, then the Sponsor or Sponsor's designee will obtain clinical study insurance against the risk of injury to clinical study participants. Refer to the Clinical Study Site Agreement regarding the Sponsor's policy on participant compensation and treatment for an injury. If the Investigator has questions regarding this policy, they should contact the Sponsor or designee.

Appendix A: Schedule of Study Procedures

Overall Study Day #	-28 to -2	-1	0	1-4	5-12	13	14	15-18	19-26	27	28	29-32	33 +/- 2
Period				1			2				3	3	
Day		0	1	2-5	6-13	14	1	2-5	6-13	14	1	2-5	15 +/- 2
					Washo	ut			Washout				
			Inpati	ent	ent		Inpatient				Inpatient		
	Screening	Check- in	Dosing			Check-in	Dosing Day			Check-in	Dosing		Follow- Up/ET¹
Informed Consent	X												
Inclusion/Exclusion Criteria	X												
Review ICF and I/E	X	X				X				X			
Demographics and Medical History	X												
Randomization ²		X											
Concomitant medications	X	X	X	X		X	X	X		X	X	X	X
Participant Admission to CRU		X				X				X			
Vital signs ³	X	X	X	X		X	X	X		X	X	X	X
Weight, height, and BMI ⁴	X												X
Urinalysis ⁵	X		X	X			X	X			X	X	X
Urine Drug Screen	X	X				X	_			X	_	_	
Cotinine Screen		X				X				X			

¹ Assessments to be completed on final in-patient day and will be repeated if AE requires in-person follow-up

² Once eligibility has been confirmed by Screening assessments ³ Assessments to include HR, BP, and temperature

⁴ Height only at screening ⁵ Part of safety assessments (Pre and 24h post-dose)

Page 62 of 64 30 Aug 2022

Physical Examination ⁶	X		X			X			X		X
Hepatitis panel and HIV antibody test	X										
Clinical laboratory tests ⁷	X	X	X	X		X	X		X	X	X
Pregnancy Test ⁸	X	X		X	X		X	X			X
FSH ⁹	X										
C-SSRS ¹⁰	X	X		X	X	X	X	X	X	X	X
ECG ¹¹	X		X			X			X		X
PK Blood Collection ¹²			X	X		X	X		X	X	
PK Urine ¹³			X	X		X	X		X	X	
Overnight Fasting		X ¹⁴			X^{15}			X^{16}			
CVN424 Dosing ¹⁷			X			X			X		
AE Assessment		X	X	X	X	X	X	X	X	X	X

⁶ Full PE at Screening, Medical Assessment pre-dose (within 24 hours prior to dosing) and 24-hours post-dose

⁷ Pre and Post dose Safety Labs, standard hematology with WBC differential, CRP, coagulation tests, lipase, amylase, albumin, and calcium. Predose labs do not need to be reviewed prior to dosing. Post dose to be done at 48 hours and EOT. Unscheduled as clinically indicated.

⁸ Serum pregnancy test at Screening and urine pregnancy test at subsequent discharge and check-ins

⁹ FSH level will be obtained on post-menopausal women (defined as continuous amenorrhea of at least 2 years and not surgically sterile)

¹⁰ Screening, Check-in, 24 and 96-hour post dose

¹¹ Triplicate standard 12-lead ECG will be recorded at Screening and on Days 0, 10, and 20 pre-dose [within 1 h prior to dosing] and 3h (+/-15 minutes) post-dose. Triplicate standard 12-lead ECG will also be recorded at Early Termination (if applicable)

¹² Plasma Sampling: Predose (within 15 minutes prior to dosing; 60 minutes for the fed treatments), 0.5, 1, 1.5, 2, 3, 4, 6, 8, 12, 16, 24, 36, 48, 60, 72, 84 and 96h

¹³ For tablet fasted sequence: Predose (for bioanalysis), 0-12, 12-24, 24-48, 48-96h. Volume of urine collected needs to be recorded

¹⁴ Sequences 1, 2, 4, 5

¹⁵ Sequences 1, 3, 5, 6

¹⁶ Sequences 2, 3, 4, 6

¹⁷ Sequences 1, 4 will be dosed with suspension; 2,3,5,6 will be dosed with tablet per figure 1

Page 63 of 64 30 Aug 2022

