16.1 Study Information

16.1.1 Protocol and Protocol Amendments

Note to File 21 October 2022

Note to File 20 October 2022

Note To File 30 September 2022

Final Protocol 30 August 2022

cerevance

NOTE TO FILE

To: Cerevance 424-102 Study Trial Master File

From: Consultant to Cerevance

Date: 21Oct2022

Study: CVN424-102

Re: Protocol Clarifications

The following are clarifications for the CVN424-102 protocol version 1.0 dated 30Aug2022.

- 9.1.5 Vital Sign Procedure
 - Clarifying that respiration rate is not needed in triplicate
 - Clarifying that the triplicate measurements at the "initial post-dose" timepoint are to be collected from 1-3 hours post administration of the study drug
 - Subsequent post-dose measurements (i.e., 24-, 48-, 72-, and 96- hours) are not needed in triplicate

Signed,

Consultant
Cerevance

NOTE TO FILE

To: Cerevance 424-102 Study Trial Master File

From: Consultant to Cerevance

Date: 20Oct2022

Study: CVN424-102

Re: Protocol Clarifications

The following are clarifications for the CVN424-102 protocol version 1.0 dated 30Aug2022.

The language in section 9.7.3 Reporting of Abnormal LFT, is to be updated as follows below. The rationale for the change is to better align with section 7.4 Criteria for Discontinuation or Withdrawal of a Participant.

Existing language:

If a participant is noted to have ALT or AST elevated >3 ×ULN on 2 consecutive occasions, the abnormality should be recorded as an AE at the discretion of the PI. In addition, an LFT increases eCRF must be completed by providing additional information on relevant recent history, risk factors, clinical signs and symptoms, and results of any additional diagnostic tests performed.

If a participant is noted to have ALT or AST >3 ×ULN and total bilirubin >2 ×ULN for which an alternative etiology has not been identified, the event should be recorded as an SAE and reported as per Section 9.7.2. The Investigator must contact the Medical Monitor to discuss the relevant participant details and possible alternative etiologies, such as acute viral hepatitis A or B or other acute liver disease or medical history/concurrent medical conditions. Follow up laboratory tests will be at the discretion of the Investigator.

To be replaced with:

If a participant is noted to have ALT or AST elevated >2 ×ULN at any point, the abnormality should be recorded as an AE.

If a participant is noted to have

[figure not shown]

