7.2 Exclusion Criteria

Any participant who meets any of the following criteria will not qualify for entry into the study:

- 1. Vegetarian, Vegan, Lactose intolerant, or follows a Kosher diet.
- 2. Evidence of clinically significant neurologic or other disorder or impairment that, in the opinion of the Investigator, is reasonably expected to impact the ability of the participant to participate or confound the study results.
- 3. A current or recent (within 6 months) gastrointestinal disease that would be expected to influence the absorption of drugs (i.e., a history of malabsorption, any surgical intervention known to impact absorption [e.g., bariatric surgery or bowel resection]). Note, history of cholecystectomy is permitted if there is no evidence of malabsorption per the Investigator.
- 4. A history of cancer or other malignancy, with the exception of low-grade cervical intraepithelial neoplasia, low-grade (low-risk) prostate cancer, or 5-year cancer-free survivors of basal or squamous cell carcinoma or higher-grade cervical intraepithelial neoplasia or prostate cancer.
- 5. A positive test result for hepatitis B surface antigen (HBsAg), hepatitis C virus (HCV) antibody, or a human immunodeficiency virus (HIV) infection at Screening.
- 6. Any clinically significant abnormalities in labs: biochemistry (including liver function test [LFT], estimated glomerular filtration rate [eGFR], and glucose), standard

- hematology with white blood cell (WBC) differential, c-reactive protein (CRP), coagulation tests, lipase, amylase, albumin, and calcium.
- 7. A supine blood pressure outside the ranges of 80 to 160 mm Hg for systolic and 50 to 100 mm Hg for diastolic, confirmed with up to two repeat tests at the Screening Visit; or symptomatic orthostatic hypotension, in the opinion of the Investigator.
- 8. A resting heart rate outside the range of 40 to 100 beats per minute (bpm) confirmed with up to two repeat tests at the Screening Visit. Note that 40-50 and 90-100 bpm may be permitted only at the discretion of the Investigator.
- 9. Positive urine result for illegal drugs at Screening and Check-In, or history of illicit drug use or alcohol abuse within 1 year prior to the Screening Visit.
- 10. Received any investigational compound (defined as a drug that has not been FDA-approved) within 30 days prior to the first dose of study medication or within 5 half-lives of the investigational compound, whichever is greater.

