7.4 Criteria for Discontinuation or Withdrawal of a Participant

Participants are free to withdraw from the study at any time upon request. The Investigator may remove a participant from the study if, in the Investigator's opinion, it is not in the best interest of the participant to continue the study. Participants may be discontinued due to the following (not inclusive):

- 1. The participant has experienced an AE that requires early termination because continued participation imposes an unacceptable risk to the participant's health, or the participant is unwilling to continue because of the AE.
- 2. Liver Function Test (LFT) Abnormalities

Study medication should be discontinued immediately with appropriate clinical follow-up (including repeat laboratory tests until a participant's laboratory profile has returned to normal/baseline status) if the following circumstances occur at any time during study medication treatment:

- Alanine aminotransferase (ALT) or aspartate aminotransferase (AST) >8 × upper limit of normal (ULN), or
- ALT or AST >5 × ULN and persists for more than 2 weeks, or
- ALT or AST >3 × ULN in conjunction with elevated total bilirubin >2 × ULN or INR >1.5, or
- ALT or AST >3 × ULN with appearance of fatigue, nausea, vomiting, right upper quadrant pain or tenderness, fever, rash and/or eosinophilia (>5%).
- 3. Significant protocol deviation. The discovery post-randomization that the participant failed to meet protocol entry criteria or did not adhere to protocol requirements and continued participation poses an unacceptable risk to the participant's health.
- 4. Lost to follow-up. The participant did not return to the clinic and attempts to contact the participant were unsuccessful. Attempts to reach the participant must be documented.
- 5. Voluntary withdrawal. The participant (or participant's legally acceptable representative) wishes to withdraw from the study. The reason for withdrawal, if provided, should be recorded in the eCRF.
 - Note: Attempts should be made to determine the underlying reason for the withdrawal and, where possible, the primary underlying reason should be recorded (e.g., withdrawal due to an AE; withdrawal due to relocation).
- 6. The Sponsor, IRB, or regulatory agency terminates the study.
- 7. Other.

Page 28 of 64 30 Aug 2022

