7.5 Procedures for Discontinuation or Withdrawal of a Participant

The Investigator must discontinue a participant's study participation at any time during the study when the participant meets the study discontinuation criteria described in Section 7.4. In addition, a participant may discontinue their participation without giving a reason at any time during the study. Should a participant's involvement be terminated, the primary criterion for termination must be recorded by the Investigator. In addition, efforts should be made to perform all procedures scheduled for the Early Termination Visit. Discontinued or withdrawn participants may be replaced at the Sponsor's discretion. Participants who withdraw from the study prior to dosing may be replaced.

Page 29 of 64 30 Aug 2022

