7.5 Clinical Laboratory Tests (Serum Chemistry, Hematology, Coagulation and Urinalysis)

Clinical laboratory tests will be measured at the following time points:

Clinical Laboratory Panels	Time Point		
	Period	CRF/Listing Day and Hour	Table
	Screening		NA
Serum Chemistry,	1, 2, 3	Day -1 Hour -26.25, -25.75	NA
Hematology, Coagulation,		Day 1 Hour -2.00, -1.75	Baseline
Urinalysis		Day 2 Hour 23.77*^	Day 2^
		Day 3 Hour 48.00^	Day 3 [^]
		Day 5 Hour 95.77*, 96.00	Day 5

Time points in the CRF/Listing column are approximated/based on the blank CRF and it should be noted that the data listings will reflect the data found in the final participant CRFs.

If applicable, an early termination assessment will be performed.

NA = Not applicable; *Period 2 is at X.75 instead of X.77, ^Urinalysis is not collected on Days 2 and 3.

Clinical laboratory results will be presented as extracted from the clinical laboratory database. Out-of-reference range flags will be recorded as follows: high (H) and low (L) for numerical results and did-not-match (*) for categorical results.

Out-of-reference range values and corresponding recheck results will be listed. Out-of-range clinical laboratory values which are deemed clinically significant will be entered, listed, and summarized with the AEs.

Clinically significant labs would be denoted as AEs and listed/summarized as such.

For all numeric laboratory values, descriptive statistics will be presented for each laboratory test by assessment time point and treatment. Change from baseline will be summarized in a

similar manner. In line with the protocol, an overall column will also be included for these descriptive statistics for which the baseline will still be the treatment specific baselines. For all numeric laboratory tests, the mean value calculated for each assessment time point and treatment will be compared to the reference range and flagged if outside of the reference range (* if above the reference range and ^ if below the reference range). In the event there is more than one reference range for a laboratory test, the comparison will be made against the lowest of the lower ranges and the highest of the higher ranges.

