7.6 Vital Signs

Vital signs will be measured at the following time points:

Parameter	Time Point		
	Period	CRF/Listing Day and Hour	Table
	Screening		NA
	1, 2, 3	Day -1 Hour -24.83	NA
Orthostatic [Blood		Day 1 Hour -0.83	Baseline
Pressure and Heart Rate].		Day 1 Hour 1.63*	Hour 1.5*
Respiration, Temperature		Day 2 Hour 24.08	Day 2
		Day 3 Hour 48.08	Day 3
		Day 4 Hour 72.08	Day 4
		Day 5 Hour 96.08	Day 5
Weight	Screening		NA (summarized in
Weight			demographics)
	3	Day 5 Hour 96.25	NA

Time points in the CRF/Listing column are approximated/based on the blank CRF and it should be noted that the data listing will reflect the data found in the final participant CRFs.

Heart rate is labeled as pulse in the CRF.

If applicable, an early termination assessment will be performed.

NA = Not applicable

Per protocol, the supine measurements are sometimes collected in triplicate. In these cases, the averaged (to the nearest tenth) of the supine measurements, collected within 15-minute window prior to the standing measurements will be used in all summaries. In the case that there are more than 3 collected in the 15-minute window, the 3 records closet to the standing will be used in the average. For time points when averages are derived, the averages will be summarized instead of the individual measurements.

Descriptive statistics will be presented for vital signs measurements by assessment time point and treatment. Change from baseline will be summarized in a similar manner. An across

^{*}Periods 2 and 3 only

summary treatment column will be included but it should be noted that the change from baseline will be treatment specific change.

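### No rule ensures that a fresh liver result is read against the section 7.4 stopping criteria before dose 2 or 3; the gap is small and cheap to close

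*Protocol*

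**What the plan says.** **Waiver.** Footnote 7 to the clinical laboratory row of Appendix A states: "Predose labs do not need to be reviewed prior to dosing". The Note to File of 30 September 2022 edits this footnote only to remove its partial list of tests. The same Note adds the waiver to the urinalysis footnote. The waiver is therefore current, and it names no sample time.

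**Schedule.** The Appendix A laboratory row is marked at the Period 1 check-in but not at the check-ins for Periods 2 and 3. Footnote 7 puts post-dose samples at 48 hours and end of treatment. SAP 7.5 lists more for Periods 1, 2 and 3: a check-in panel ("Day -1 Hour -26.25, -25.75"), a baseline panel about 2 hours before the dose, and panels at about 24, 48 and 96 hours after it.

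**Stopping rule.** Section 7.4 says of its liver criteria: "Study medication should be discontinued immediately with appropriate clinical follow-up". Section 7.5 obliges the Investigator to act "when the participant meets the study discontinuation criteria described in Section 7.4". The Note of 20 October 2022 makes the same liver criteria serious adverse events. It also says that ALT or AST "elevated >2 ×ULN at any point, the abnormality should be recorded as an AE".

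**Other provisions.** Appendix A marks "Review ICF and I/E" at all three check-ins, and exclusion 6 covers liver tests. Section 9.1.11 requires laboratory reports to be signed as reviewed, with no deadline. It also requires a retest within 7 days once ALT or AST above 3 × ULN is found. Footnote 6 requires a medical assessment in the 24 hours before dosing.

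**The concern.** Section 7.4 makes discontinuation mandatory, but it can act only on a result that someone has read. Before dose 1, Appendix A gives an unexposed participant a check-in panel. Before doses 2 and 3, when the participant has already received the drug, it gives only the dosing-day sample, which need not be read first.

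Some 7.4 criteria can be met on one blood draw without symptoms. They include ALT or AST above 8 × ULN, and ALT or AST above 3 × ULN with total bilirubin above 2 × ULN or INR above 1.5. A participant could meet one of these on a sample already taken and still receive the next 150 mg dose with every written rule followed. What is at stake is participant safety. No pharmacokinetic endpoint or estimate is affected.

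**Working it through.** The plan gives no figure to reproduce. The check is a comparison of provisions plus simple time arithmetic.

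**1. Reading the laboratory row.** In the part of Appendix A that holds this row, the two washout columns drop out and 11 columns remain. The dosing row is marked in columns 3, 6 and 9, and the pregnancy-test row falls on screening, check-ins and discharges as its own footnote describes, so the columns line up. The laboratory row is marked in columns 1–4, 6, 7 and 9–11. The blanks, columns 5 and 8, are the check-ins for Periods 2 and 3.

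The SAP restricts a time point to certain periods when it means to: in SAP 7.6 one vital-sign time carries "Periods 2 and 3 only". The Day -1 laboratory panel has no such restriction.

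**2. Age of the newest scheduled panel at doses 2 and 3, leaving out the same-day sample.** Doses fall on Study Days 0, 14 and 28.

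| Source | Panel | Age at next dose |
|---|---|---|
| Appendix A, footnote 7 | 48 h (Study Day 2) | 14 − 2 = 12 days |
| SAP 7.5 | Day 5, 96 h (Study Day 4) | 14 − 4 = 10 days |
| SAP 7.5 | Day -1 | 26.25 or 25.75 h |

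The intervals before dose 3 are the same.

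**3. What each safeguard reaches.**

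| Provision | What it leaves open |
|---|---|
| Post-dose panels at about 24, 48 and 96 h (SAP 7.5) | A rise that starts later |
| Retest above 3 × ULN (9.1.11) | Needs an abnormality already found |
| Adverse event recording above 2 × ULN (Note, 20 October 2022) and follow-up (9.7.1.2) | Needs a known abnormality; no pre-dose deadline |
| Signed review of reports (9.1.11) | No deadline |
| Eligibility review at check-in, with exclusion 6 | Orders no new sample; does not name 7.4 |
| Medical assessment before dosing (footnote 6; SAP 7.9) | Does not detect a silent laboratory change |
| Unscheduled laboratory tests (footnote 7) | Need a clinical prompt |

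None of these orders a fresh liver result and has it read before dose 2 or 3.

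**4. Early elevations.** If a value above 3 × ULN is read on the day of the draw, the retest is due by Study Day 2 + 7 = 9 (48 h panel) or 4 + 7 = 11 (Day 5 panel). Both precede Day 14. The 7 days run from when the abnormality was found, so the retest stays ahead of dose 2 if the 48 h result is read within 14 − 9 = 5 days, or the Day 5 result within 14 − 11 = 3 days. With an in-house laboratory, that is a fair expectation.

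**5. Drug remaining.** The half-life is about 33 h (section 4.1). A single-exponential approximation gives fraction left = 2^(−t/33).

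- 48 h: 48/33 = 1.45 half-lives, about 36% left.
- 96 h: 96/33 = 2.91 half-lives, about 13% left.
- 336 h (next dose): 336/33 = 10.2 half-lives, about 0.09% left.

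Some exposure follows the last post-dose panel, but very little is left late in washout.

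**6. Time available for a result.** In the fed arm the meal starts about 0.5 h before dosing. A Day -1 draw leaves 25.75 − 0.5 = 25.25 h to 26.25 − 0.5 = 25.75 h. The draw at Hour -2.00 or -1.75 leaves 1.5 or 1.25 h. This supports waiving review of the same-day sample but not of the Day -1 panel.

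**The case against.** The best defence is that the waiver is deliberate and ordinary. The sponsor edited footnote 7 in September 2022, kept the sentence and extended it to urinalysis. The SAP labels the Hour -2 sample as baseline, and not waiting for a same-day baseline sample is normal logistics. The SAP says its laboratory times are approximated from the blank CRF, so the Day -1 panel was probably drawn in every period and would be about 26 hours old at dosing.

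The safeguards in the working leave only a symptom-free rise late in washout. The earlier data show no liver concern: section 4.1 reports no treatment-related laboratory trend in healthy volunteers, who received up to 7 daily doses of up to 150 mg, and no notable laboratory changes in Phase 2.

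Most of this stands, and it is why the point is minor. It does not supply the missing rule. If footnote 7 means only the Hour -2 sample, it does not say so, and neither document requires the Day -1 panel to be read before dosing.

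A reader might infer three stronger things that the documents do not support:

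- **That review before dosing is barred.** It is only not required, and the Investigator remains free to read any result.
- **That participants go 12 days without a liver test.** That figure takes Appendix A alone and counts only the 48 h panel. It leaves out the Day 5 and Day -1 panels in the SAP, and the end-of-treatment panel in footnote 7 is not given a day.
- **That the protocol and SAP are proven to schedule different blood draws.** The CRF that would settle this is not among the documents.

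**Conclusion.** The point holds as a cheap improvement. The footnote 7 waiver has no stated limit, Appendix A does not schedule the Period 2 and 3 check-in panel that SAP 7.5 lists, and no provision ensures that a fresh liver result is read against 7.4 before dose 2 or 3.

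The gain is small. The case left uncovered is rare, symptom-free and late-arising, with about 0.1% of the drug left at re-dosing. The documents give no frequency for it, and none is estimated here. It would go too far to conclude that the trial carries a liver hazard or that 7.4 cannot work, because the earlier data show no signal and abnormalities found soon after dosing are followed.

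The conclusion rests on the column reading of Appendix A, on the reported half-life with a single-exponential decline, and on prompt reading of post-dose results. Confidence is medium, mainly because the CRF is not available.

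**What to change.** 1. In the Appendix A laboratory row, mark the check-in panel for Periods 2 and 3, matching Period 1 and SAP 7.5.
2. Require ALT, AST, total bilirubin and INR from that panel to be checked against section 7.4 before doses 2 and 3.
3. State in footnote 7 that the waiver covers only the same-day baseline sample taken about 2 hours before dosing.

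Keep the Hour -2 sample as the baseline. Moving that draw to check-in is not advised, because it would replace a 2-hour baseline with a 26-hour one and require SAP 7.5 to be relabelled.

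The text change is two marks, one added requirement and one clarified sentence. The laboratory is in-house, with about 25 hours to produce the result. The downside is an occasional dose delay. If the Day -1 panel is already drawn, no extra blood is needed. If it is not, assuming 5–10 mL per draw (the documents give no tube volume), two draws add 10–20 mL per participant: 10/500 = 2% to 20/500 = 4% of the 500 mL limit in section 9.5. Thresholds, sample size and the pharmacokinetic analysis do not change, and clinical decisions stay with the sponsor and the Investigator.
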